9 DATA HANDLING AND RECORD KEEPING

9.1 Data Capture

The following source data may be generated and handled for further data basing process:

- Paper-based or electronic data captured in Case Report Forms
- Paper-based or electronic data captured systems, other than the case Report Forms
- Paper or electronic data from local or external vendors.

To ensure accurate, complete, and reliable data, the Sponsor or its representative will provide instructional material to the study site(s), as appropriate. Training session will be given during a start-up/initiation meeting for instructions on the completion/data entry of any source data documents and electronic Case Report Forms.

The Investigators or their designees must verify that all data entries in the eCRFs are accurate and correct. If certain information is not available for a particular timepoint and/or subject, specific instructions should be followed, e.g. to document that the procedure was either not done (ND) or not applicable (NA).

Every effort should be made to ensure that all safety evaluations are completed by the same individual who made the initial baseline determination.

9.2 Data Handling

All or part of the data will be monitored at periodic visit to the study site, according to a monitoring plan. All entries in the eCRFs, corrections and alterations are to be made by the responsible Investigator or his/her designee.

Once monitored and cleaned, the paper-based data (either source or transcribed data) that have been selected for populating the database will follow a single entry process. Electronic data will be directly entered in the database.

Details of all data management procedures, from the initial planning to the archiving of final datasets/documents following database freeze/lock will be documented in appropriate data management and validation plan(s). Among others, these procedures will also describe quality control checks, data handling process for any missing, unused or spurious data, as well as coding procedures for AE's, medical history, physical examination and medications.

9.3 Record Keeping

The Investigator will keep records of all original source data. This might include laboratory tests, medical records, and clinical notes.

Depending on the data collected and the type(s) of data, records will be kept following storage, and archiving procedures agreed by the Sponsor/Investigator site involved in this study, and in accordance to any regulations that are applicable in the country(ies) where the study is conducted.

10 REGULATORY AND ETHICAL CONSIDERATIONS

The study will be conducted in compliance with independent ethics committees/institutional review boards (IECs/IRBs), informed consent regulations, the Declaration of Helsinki and International Conference on Harmonisation (ICH) Good Clinical Practice (GCP) Guidelines. Any episode of noncompliance will be documented. The Electronic Data Capture (EDC) system will comply with the Food and Drug Administration (FDA), 21 CFR Part 11, Electronic Records, Electronic Signatures, and FDA, Guidance for Industry: Computerised Systems Used in Clinical Trials.

In addition, the study will adhere to all local regulatory requirements.

10.1 Subject Information Sheet and Consent

The Investigator is responsible for ensuring that the subject understands the potential risks and benefits of participating in the study, including answering, orally and/or in writing, to any questions the subject may have throughout the study and sharing any new information that may be relevant to the subject's willingness to continue his or her participation in the study in a timely manner.

The subject information sheet and consent document will be used to explain the potential risks and benefits of study participation to the subject in simple terms before the subject is entered into the study, and to document that the subject is satisfied with his or her understanding of the study and desires to participate.

The Investigator is ultimately responsible for ensuring that the Ethics Committee (EC) approved informed consent is appropriately signed and dated by each subject prior to the performance of any study procedures. Informed consent obtained under special circumstances may occur only if allowed by local laws and regulations.

10.2 Ethical Review Considerations

The following documents should be submitted to the relevant ECs for review and approval to conduct the study (this list may not be exhaustive):

- Protocol/amendment(s) approved by the Sponsor,
- Currently applicable SmPC or package labelling,
- Relevant Investigator's curriculum vitae,
- Subject information and informed consent document(s) and form(s),
- Subject emergency study contact cards
- Recruitment procedures/materials (advertisements), if any.

The EC(s) will review all submission documents as required, and a written favourable opinion for the conduct of the study should be made available to the Investigator before initiating the study. This document must be dated and clearly identify the version number(s) and date(s) of the documents submitted/reviewed and should include a statement from the EC that they comply with GCP requirements.

The study may begin at the investigative site(s) only after receiving this dated and signed documentation of the EC approval or favourable opinion.

During the study, any update to the following documents will be sent to the EC either for information, or for review and approval, depending on how substantial the modifications are: (1) SmPC; (2) reports of SAEs; (3) all protocol amendments and revised informed consent(s), if any.

At the end of the study, the Ethics Committee will be notified about the study completion.

10.3 Regulatory Considerations

This study will be conducted in accordance with applicable laws and regulations, GCPs, and the ethical principles that have their origin in the Declaration of Helsinki.

All or some of the obligations of the Sponsor will be assigned to a Clinical Research Organisation (CRO).

An identification code assigned to each subject will be used in lieu of the subject's name to protect the subject's identity when reporting AEs and/or other trial-related data.

10.4 Final Report Signature

The Investigator or designee will proposed to review and sign the clinical study report for this study, indicating agreement with the analyses, results, and conclusion of the report.

11 INSURANCE AND FINANCE

11.1 Insurance

The Sponsor declares that it has taken out a product liability insurance covering all subjects screened and enrolled in this study in respect to risks involved in the study.

11.2 Financial Agreement

Since this study is to be performed in partnership with a CRO, separate financial agreements between the Sponsor and the CRO on one side, and the CRU and the CRO on the other side, will be signed prior to initiating the study, outlining overall Sponsor and Investigators responsibilities in relation to the study.

12 QUALITY CONTROL AND QUALITY ASSURANCE

To ensure accurate, complete, and reliable data, the Sponsor or its representatives will provide instructional material to the study sites, as appropriate. A start-up training session will be done prior to screening start to instruct the Investigators and study coordinators. This session will give instruction on the protocol, the completion of the eCRFs, and all study procedures.

12.1 Protocol Amendments and Protocol Deviations and Violations

12.1.1 Protocol Amendments

No changes from the final approved (signed) protocol will be initiated without the prior written approval or favourable opinion of a written amendment by the IEC/IRB, except when necessary to eliminate immediate safety concerns to the subjects or when the change involves only logistics or administration. The principal Investigator and the Sponsor will sign the protocol amendment.

12.1.2 Protocol Deviations, Violations, and Exceptions

A protocol deviation is a nonadherence to protocol specific study procedures or schedules that does not involve inclusion/exclusion criteria, primary objective evaluation criteria, and/or GCP guidelines. Deviations are considered minor and do not impact the study.

A protocol violation is any significant divergence from the protocol, i.e. a nonadherence on the part of the subject, the Investigator, or the Sponsor to protocol specific inclusion/exclusion criteria, primary objective evaluation criteria, and/or GCP guidelines. Protocol violations will be identified and recorded, by clinical unit personnel in the eCRF.

As a matter of policy, the Sponsor will not grant exceptions to protocol-specific entry criteria to allow subjects to enter a study. If under extraordinary circumstances such action is considered ethically, medically, and scientifically justified for a particular subject, prior approval from the Sponsor and the responsible IRB/IEC is required before the subject will be allowed to enter the study.

If investigative clinical unit personnel learn that a subject who did not meet protocol eligibility criteria was entered in a study (protocol violation), they must immediately inform the Sponsor. Such subjects will be discontinued from the study, except in an exceptional instance, following review and written approval by the Sponsor and the responsible IRB/IEC.

12.1.3 Information to Study Personnel

The Investigator is responsible for giving information about the study to all staff members involved in the study or in any element of subject management, both before starting any study procedures and during the course of the study (e.g. when new staff become involved).

The Investigator must assure that all study staff members are qualified by education, experience, and training to perform their specific responsibilities. These study staff members must be listed on the clinical unit authorisation form, which includes a clear description of each staff member's responsibilities. This list must be updated throughout the study, as necessary.

The study monitor is responsible for explaining the protocol to all study staff, including the Investigator, and for ensuring their compliance with the protocol. Additional information will be made available during the study when new staff become involved in the study and as otherwise agreed upon with either the Investigator or the study monitor.

12.2 Monitoring

The Investigator is responsible for the validity of all data collected at the site.

The Sponsor is responsible for monitoring these data to verify that the rights and well-being of subjects are protected, study data are accurate (complete and verifiable to source data), and that the study is conducted in compliance with the protocol, GCP, and regulatory requirements.

Before the study initiation visit, the Sponsor assigned study monitor will write a monitoring plan indicating the monitoring procedures and at which occasions during the study monitoring visits will be performed.

Periodic visits will be made to the study site throughout the study at mutually agreeable times. Any appropriate communication tools will be set up to ensure the Sponsor and/or its representative is/are available for consultation, so they can stay in contact with the study site personnel.

Adequate time and space for monitoring visits should be made available by the Investigator.

The Investigator will allow direct access to all relevant files (for all subjects) and clinical study supplies (dispensing and storage areas) for the purpose of verifying entries made in the eCRF, and assist with the monitor's activities, if requested.

Quality of the paper-based or electronic data will be reviewed to detect errors in data collection and, if necessary, to verify the quality of the data.

The eCRF is expected to be completed an ongoing basis to allow regular review by the study monitor, both remotely by the internet and during site visits. The study monitor will use functions of the electronic data capture (EDC) system to address any queries raised while reviewing the data entered by the study site personnel in a timely manner.

Whenever a subject name is revealed on a document required by the Sponsor (e.g., laboratory print outs) the name must be blacked out permanently by the site personnel, leaving the date of birth visible, and annotated with the subject number as identification.

12.3 Investigator's Regulatory Obligations

All clinical work under this protocol will be conducted according to GCP rules. This includes that the study may be audited at any time by a Quality Assurance personnel designated by the Sponsor, or by regulatory bodies. The Investigator must adhere to the GCP principles in addition to any applicable local regulations.

If requested, the Investigator will provide the Sponsor, applicable regulatory agencies, and applicable Ethics Committee with direct access to any original source documents.

The Investigator(s) should demonstrate due diligence in recruitment and screening of potential study subjects. The enrolment rate should be sufficient to complete the study as agreed with the Sponsor. The Sponsor should be notified of any projected delays, which may impact the completion of the study.

12.3.1 Audit and Inspection

Authorised personnel from external CAs and the Sponsor's authorised quality assurance personnel may carry out inspections and audits.

12.3.2 Data Quality Assurance

Monitored eCRF, transferred from the clinical unit to the assigned data management group, will be reviewed (secondary monitoring) for completeness, consistency, and protocol compliance.

Reasons should be given in the relevant eCRF for any missing data and other protocol deviations. Any electronic queries and items not adequately explained will require additional electronic manual queries to be raised to the Investigator for clarification/correction. The

13 PUBLICATION POLICY

The Sponsor encourages acknowledgement of all individuals/organisations involved in the funding or conduct of the study, including medical writers or statisticians subject to the consent of each individual and entity concerned, including acknowledgement of the Sponsor.

The results of this study may be published or communicated to scientific meetings by the Investigators involved in the study. For multicentre studies, a plan for scientific publication and presentation of the results may be agreed and implemented by the study Investigators or a steering committee. The Sponsor requires that reasonable opportunity be given to review the content and conclusions of any abstract, presentation, or paper before the material is submitted for publication or communicated. This condition also applies to any amendments that are subsequently requested by referees or journal editors. The Sponsor will undertake to comment on the draft documents within the time period agreed in the contractual arrangements, including clinical trial agreements, governing the relationship between the Sponsor and authors (or the author's institution). Requested amendments will be incorporated by the author, provided they do not alter the scientific value of the material.

If patentability would be adversely affected by publication, this will be delayed until (i) a patent application is filed for the content of the publication in accordance with applicable provisions of the clinical trial agreement concerned, (ii) the Sponsor consents to the publication, or (iii) the time period as may be agreed in the contractual arrangements, including clinical trial agreements, governing the relationship between the Sponsor and authors (or authors' institution) after receipt of the proposed publication by the Sponsor, whichever of (i), (ii) or (iii) occurs first.

The author undertakes to reasonably consider the Sponsor's request for delay to the proposed publication should the Sponsor reasonably deem premature to publish the results obtained at the then stage of the study.

15 ATTACHMENTS

15.1 Attachment 1 – Study Schedule

CONFIDENTIAL – Protocol n°: D-FR-00250-108 v.4.0 Date: 07-SEPT-2016 Page 53 of 66

Study Schedule of Events - Protocol D-FR-00250-108

	Study	Study Students of Events - Flower D-Fix-00230-100	112 - 110	10001	D-LIN-	-00700	00					
	Screening			Trea	Treatment Period	eriod				I	Follow up Period	Period
Weeks:		1			2	3	4	5	5	6	13	17
Visits:	V1	V2			V3	V4	V5	9/	77	8/	6/	V10 (EOS)
Days:	D-42 to D-21	D-1 (Baseline)	D1	D2	D8	D15	D22	D29	D35	D65	D95	D125
Time windows:		+/- 15 min	in		+/- 1d	+/- 1d	+/-1d	+/- 1d	+/- 1d	p/ -/+	p/ -/+	p/ -/+
Subjects' disposition:	Outpatient	Inpatient	ıt		out	out	out	ont	inpat	inpat	inpat	out
				,								
Informed Consent, Demography, Medical & Surgical History, Prior Medications	X											
Safety Evaluations												
Physical exam (incl. Body Height/Weight °) and Vital Signs, aural body temperature	X											X
12-lead Electrocardiograms (ECGs)	×											×
Concomitant Medication & Adverse Events	X	X	X	X	X	X	X	X	X	X	X	X
Safety Laboratory (Haematology, Biochemistry, Coagulation and Urinalysis)	х×	X										X
Pregnancy Test (WOCBP only) ^d	X	X										X
Urine Drug Assay & Alcohol test	X	X										
Smecta® (TID, morning, noon, evening)			X _h						X _h			
Biological Samples												
Blood Samples for Elemental Impurities and biobanking	X	X	$X^{a,e}$	Xp	X^b	$X_{\rm p}$	Xp	X_{b}	$X^{a,e}$	X	X	X
Urine Collection (24-hour) for Elemental Impurities		X							X	X	×	
Faecal Samples for Microbiota	Xg	X			X				X	X	X	X
Consistency of stools (Bristol scale) and frequency over 24h by subject ^k	ΣX	×			X				×	×	×	×
a Six samples on Day 1 (and Day 35): 2 hours after the first dose (ex.: Smecta® intake 7.00am, meal 7.30am, PK 9.00am), immediately before second dose (ex.: PK	2 hours after the	ne first dose (ex.: Sme	cta® inta	ake 7.00	Jam, mea	1 7.30an	1, PK 9.0	0am), im	mediately	before se	cond dose	(ex.: PK

SIX samples on Day 1 (and Day 52): 2 nours after the first dose (ex.: Smecta@ make 7.00am, meal 7.30am, FN 9.00am), immediately before second dose (ex.: FN 11.30am, Smecta@ intake just after at 11h.30, meal at 12.30), 3h post lunch dose (ex.: PK at 2.30pm), immediately before the third dose (ex.: PK at 6.30pm, Smecta® intake just after at 6.30pm and meal 7.30pm), 3h post evening dose (ex.: PK at 9.30pm) and 6h post evening dose (ex.: 00.30am), and one sample on Day 36 in the morning (ex.: PK at 7.00am, Smecta® intake just after at 7.00am and meal 7.30am)

On pre-dose before dosing (morning, approximately 7am on Day 2, and on pre-dose of any of the dosing occasion on the other days)

b On pre-dose before dosing (mcc Body height only at screening.

- Pregnancy test: serum at screening and urine at baseline and EoS.
 - Time window for PK sampling: $\pm 15 \text{ min}$ To be performed 24h before the visit 3
- l sample to be taken at screening visit at the CRU and 1 sample by the subject at home at Day-14 ±1 day
- Smecta® should be taken fasting and at least one hour before meal, except for breakfast at least 30 minutes before.
- C-reactive protein to be analysed only at screening м т. т. т. ж
- Diary to be completed at screening retrospectively to cover the past 24h, and 24h before the Day-14 stool sample To the extent possible, to collect the data over approximately 24h preceding the stool sample taken at the visit 24h (i.e. 1 day or more).

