3.3.1.3 Treatment Period

The treatment period will occur from Day 1 (first intake in the morning) to Day 35 (last intake in the evening) and subjects will be required to attend the CRU on several occasions during the treatment period:

- Day 1 (Visit 2): The subjects will be dosed within the unit with Smecta® at breakfast, lunch and dinner time, PK samples will be collected as described in the Schedule of events (see Attachment #1_Section 15.1) and the subject will leave the unit on Day 2 after PK sampling and Smecta® administration in the morning. Subjects will receive a box containing Smecta® treatment for a bit more than 2 weeks (20 days) as well as a diary to record the drug administration and consistency and frequency of stools at the day before the Day 8 visit.
- Out-patient visits (Visits 3 to 6): the subjects will be required to come back to the CRU for out-patient visits on Days 8, 15, 22 and 29 for blood sampling for impurities dosing and the review of adverse events and concomitant medication. One day before Day 8, subject will need to complete the diary with assessment of consistency and frequency of stools using the Bristol scale. During those visits, stools will be collected only on Day 8. At Day 22 the subjects will receive a second box containing Smecta® treatment for the last 2 weeks.
- Days 35-36 (Visit 7): Subjects will come back to the CRU in the morning of Day 35 (or the evening before for convenience) in order to start the process to collect urine samples, blood and stools sampling. They will be dosed with Smecta® at breakfast,

lunch and dinner. They will leave the unit in the morning of Day 36 after the completion of the 24-hour urine collection and PK sample in the morning.

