3.3.3 Study Duration

For each individual subject, the study is expected to last approximately 5,5 months, including up to 42 days for screening assessments, 35 days of treatment and a 3-month post-treatment follow-up period.

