5.1.2 Study Drug Administration

The Investigator, or designee, will only dose and allocate Smecta® treatment to subjects enrolled in this study.

Two kits of Smecta® will be prepared and provided to subject(s) according to the predetermined dosing schedule agreed upfront with the Sponsor or designee; each kit consisting of one box, containing 60 sachets of Smecta® covering the administration for 20 days.

Each subject will be instructed to ingest Smecta® at three occasions, in the morning, at noon and in the evening, and every day until the Day 35 visit included. In order to standardize the conditions of administration of Smecta® and potentially limit the variability and increase bioavailability of lead all along the trial, Smecta® should be taken in fasting and at least one hour before meal, except for breakfast at least 30 minutes before.

The actual time of dosing of all Smecta® ingestions will be recorded by the subject on his/her own Diary as well as the start and ending time of the meals, and reported by the site in the eCRF, or will be recorded by the site when applicable in the eCRF.

Subjects will be instructed to contact the Investigator as soon as possible if he/she has a complaint or problem with the study drug so that the situation can be assessed.

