7.3.1 Sampling Schedule

Urine collections (as 24-hour collection) and Blood samples for the measurement of elemental impurities will be collected as described in the Schedule of events (see Attachment #1_Section 15.1).

During the outpatient visits, blood samples will be collected pre-dose of any of the 3 dosing occasions of that day.

Taken into account the time window flexibility during the Day 35, the 24-hour urine collection should be done whilst subject is still under study treatment (e.g.: if subject performs the Day 35 at Day 36, Smecta® will be given until the evening of Day 36, or alternatively if subject comes at Day 34, the last Smecta® intake will be done at Day 34 evening).

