7 APPENDICES TO THE SAP TEMPLATE

Appendix 1: Derived Data

The following derived data will be calculated:

(1) Study day

Study day will be defined as ‘-1’ for the day prior to IMP administration and as ‘1’ for the day of IMP administration (i.e. day 0 does not exist).

(2) Study duration

Study duration (weeks) will be calculated as [(last visit attended - date of first IMP administration) + 1] / 7.

(3) Study drug exposure

Study drug exposure (weeks) will be derived using information from diary and will be calculated as [(last date of IMP administration - first date of IMP administration) + 1] / 7.

(4) Compliance

Compliance (%) will be calculated as (the total number of sachets taken / the total number of expected sachets to be taken) x 100.

The total number of sachets taken will be derived using information from diary as the sum of number of sachets taken when a date of IMP administration is entered.

The total number of expected sachets to be taken will be derived using information from diary based on three sachets per day (TID) (morning, noon, and evening) to be taken by the subject as [(last date of IMP administration - first date of IMP administration) + 1] x 3.

(5) Baseline

BLL baseline will be derived as the average between the available screening and pre-dose (Day-1) values.

Baseline for other parameters will be derived as the last available (and reliable if applicable) assessment before IMP administration.

(6) Absolute change from baseline

Absolute change from baseline will be calculated as the difference from baseline (e.g. assessment at the visit – assessment at baseline).

(7) Ae parameter

Ae parameter (ng) will be calculated as the cumulated concentration of EI in urine × the total volume of urine collected over 24 hours.

(8) Therapeutic Class

The therapeutic class will correspond to the first 3 digits of the ATC code. The decoding of the therapeutic class will be done from the WHO-DD June 2016 Version or higher.

(9) Prior and concomitant medication duration

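### The schedule footnote describes a Smecta intake after the Day 36 morning sample, while the protocol text ends dosing on the evening of the Day 35 visit; the two must be reconciled in protocol and SAP

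*Protocol*

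**What the plan says.** Footnote a of the schedule, in protocol Attachment 1 (15.1), gives the sampling times for Day 1 and Day 35 and then adds "one sample on Day 36 in the morning (ex.: PK at 7.00am, Smecta® intake just after at 7.00am and meal 7.30am". SAP 1.3.3 repeats it word for word.

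The body of the protocol ends dosing earlier:

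- Section 3.3.1.3 sets the treatment period "from Day 1 (first intake in the morning) to Day 35 (last intake in the evening". For the last inpatient morning it says "They will leave the unit in the morning of Day 36 after the completion of the 24-hour urine collection and PK sample in the morning", with no dose. For Day 2 the same section does name a dose before discharge.
- Section 5.1.2 has subjects take the product "every day until the Day 35 visit included".
- Section 7.3.1 covers a visit moved within its window: "if subject performs the Day 35 at Day 36, Smecta® will be given until the evening of Day 36". For a Day 34 visit, the last intake is that evening.
- Section 3.3.3 counts "35 days of treatment and a 3-month post-treatment follow-up period".

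On the analysis side, SAP 3.2.2.1 summarises changes from baseline and, additionally for the follow-up time points, changes from the Day 36 morning value. SAP Appendix 1 (3) derives exposure in weeks from the first and last administration dates. Appendix 1 (4) derives expected sachets as "last date of IMP administration - first date of IMP administration) + 1] x 3".

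**The concern.** The study measures lead from the product, so the end of exposure is a basic fact, and the documents give two answers. Protocol 3.3.1 and 7.3.1 send sites to Attachment 1 for procedures and sampling, so the footnote can be acted on. No rule says which passage prevails. It is therefore unclear whether taking or omitting a sachet on the morning of Day 36 is a deviation.

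Three reported quantities depend on the answer: the number of doses and weeks of exposure, the compliance percentage, and the meaning of the change from Day 36. Under the footnote, one dose falls after the reference sample and so inside an interval presented as post-treatment.

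**Working it through.** **Inputs.** Three sachets a day (protocol 5.1.2); first dose on Day 1 and last on Day 35 (3.3.1.3); visit window of ±1 day (Attachment 1, with the dosing rule in 7.3.1); two kits of 60 sachets (5.1.2); about 46.35 µg lead per day at three sachets (1.7); study batch of about 4.7 µg/g in 3 g sachets (5.1.1); blood half-life of about 40 days (1.7); SAP Appendix 1 (3) and (4).

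**The plan's own figure.** Day 1 to Day 35 is 35 − 1 + 1 = 35 days, or 35/7 = 5.00 weeks, as stated. Sachets: 35 × 3 = 105.

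**Both readings, for a visit held on Day 35:**

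| | Text | Footnote |
|---|---|---|
| Sachets taken | 105 | 105 + 1 = 106 |
| Dosing dates | 35 | 36 |
| Exposure (weeks) | 35/7 = 5.00 | 36/7 = 5.14 |
| Expected sachets (dates × 3) | 105 | 108 |
| Compliance, perfect taker | 105/105 = 100% | 106/108 = 98.1% |

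**Can the visit window explain the footnote?** No. Under 7.3.1 the last dose is on the evening of the visit day, whether that is Day 34, 35 or 36. No position of the visit puts a dose after the next-morning sample. The window does widen exposure by itself: 34 to 36 days, or 34 × 3 = 102 to 36 × 3 = 108 sachets.

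**Supply.** 2 × 60 = 120 sachets against 105 needed leaves 15. Supply would not prevent a further dose, but that does not show that one would be given.

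**Lead in one sachet.** 46.35/3 = 15.45 µg, or 4.7 × 3 = 14.1 µg for the study batch. This is ingested lead; protocol 1.7 says the bioavailable share is unknown. One sachet in 105 is 0.95%.

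**Carry-over to follow-up.** Assume one-compartment decay with a 40-day half-life and the same absorbed fraction for every sachet. At Day 65:

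- The 105 scheduled sachets leave 3 × Σ 0.5^((65 − d)/40), for d = 1 to 35, which is 47.2 sachet-equivalents.
- One sachet on Day 36 leaves 0.5^(29/40) = 0.605.
- The ratio is 0.605/47.2 = 1.3%.

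Under this model both terms decay at the same rate, so the ratio is the same at Days 95 and 125. It is a share of the treatment-attributable increment, not of total blood lead.

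**What is untouched.** The Day 36 sample is drawn before the intake that the footnote describes, so that value and all earlier values are the same under either reading.

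**The case against.** The footnote is a weak source for a dosing instruction. It is attached to the blood-sample row, not the Smecta row, and the grid has no Day 36 column. The intake appears only inside a clock-time example, and may be a carry-over from the Day 2 pattern of sample then dose. The sections on treatment period, administration and duration agree with each other. This explains how the conflict could have arisen. It does not remove it, because the wording is current in both documents.

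The numerical case against a large effect also stands:

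- The window already allows 102 to 108 sachets, so 106 sachets or 36 days lies inside the permitted range.
- 98.1% stays in the 80–120% compliance category of SAP 3.2.9, and no passage ties a shift of two points to membership of an analysis population.
- Counting dates times three over-counts any partial last day, whatever the footnote says. It is a small weakness of the formula in its own right.
- All administrations are already to be listed by subject and date (SAP 3.2.9, Listing 16.2.5.1), so a Day 36 intake would be visible.

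A reader might also infer that the two centres would dose differently and so bias the lead results by country. The documents do not support that. Both centres work from one protocol, nothing suggests they would read it differently, and the by-country display is descriptive with no significance testing (SAP 3.1.6 and 3.2.20).

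**Conclusion.** The contradiction is real and stands in the current text of both documents. It is an internal inconsistency with small consequences: one sachet in 105, 0.14 weeks of exposure, and a perfect taker shown at 98.1% under the footnote reading. These figures assume a visit on Day 35 exactly. The 1.3% at Day 65 rests on the one-compartment and equal-absorption assumptions.

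Two stronger readings should be set aside. The SAP does not define the Day 36 morning value as the start of follow-up. It is a reference added to the change from baseline, which remains the primary endpoint (SAP 3.1.1). Nor do the documents show that any subject took a dose after that sample. The sample size and the changes from baseline through Day 36 do not depend on the answer. Correction is still worthwhile, because the conflict sits in the operational schedule and costs almost nothing to remove.

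**What to change.** 1. Reconcile footnote a, in protocol Attachment 1 and SAP 1.3.3, with protocol 3.3.1.3, 5.1.2 and 7.3.1. All should state the same last dose relative to the Day 35 visit and its ±1 day window, and say whether anything is taken on the following morning. Which rule applies is for the sponsor to state.
2. In SAP Appendix 1 (4), derive expected sachets from scheduled dosing occasions instead of calendar dates times three. A subject with 106 sachets would then show 106/106 = 100% if that morning is a scheduled occasion, or 106/105 = 101.0% if it is not.
3. If any dose was taken after the Day 36 morning sample, identify the subjects from the administration listing already planned and footnote them in the change-from-Day-36 table.

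The cost is one footnote in two documents, one line in the derivation and, if needed, one table footnote. No new data are required. If dosing is already complete, items 2 and 3 can still be done.
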